5.1.5 Statistical Methods for Observational Objective(s)

5.1.5.1 Immunogenicity

No hypotheses will be tested. Descriptive statistics will be presented.

The meningococcal serogroups A, C, Y, and W measured by rSBA in a subset of subjects in all groups at Day 0 (before Dose 1) (all groups), 30 days after Dose 2 (Groups 1, 2, and 3) or 30 days after Dose 3 (Group 4) in infancy, and before and 30 days after the booster dose (all groups) will be described with:

- GMT and 95% CI
- Titer distribution and RCDCs
- Percentage of subjects with titer $\geq 1:8$ and $\geq 1:128$ and 95% CI
- Percentage of subjects with titer ≥ 4 -fold rise from pre-vaccination to post- vaccination and 95% CI
- Percentage of subjects with rSBA vaccine seroresponse and 95% CI

5.1.5.2 Safety

Safety results will be described for subjects in all study groups after any and each vaccination at 2, 4, 6 (only for Group 4) and 12 to 18 months of age (Visits 1, 2, and 4 for Groups 1, 2 and 3, and Visits 1, 2, 3 and 5 for Group 4). The main parameters for the safety endpoints will be described by 95% CI using the exact binomial method (Clopper-Pearson method).

At least the following parameters will be presented:

- Unsolicited systemic AEs reported in the 30 minutes after each vaccination, including occurrence, nature (Medical Dictionary for Regulatory Activities [MedDRA] preferred term), duration, intensity, action taken, relationship to the product administered, and whether the event caused termination from the study.
- Solicited (prelisted in the subject's diary card and CRB) injection site and systemic reactions starting any time from Day 0 (day of vaccination) through Day 7 after each vaccination,

including occurrence, time of onset, number of days of occurrence, intensity, action taken, and whether the reaction caused termination from the study.

- Unsolicited non-serious AEs reported up to 30 days after each vaccination, including occurrence, nature (MedDRA preferred term), time of onset, duration, intensity, action taken, relationship to the product administered, and whether the event caused termination from the study.
- SAEs (including AESIs) reported throughout the study, ie, from Visit 1 (first vaccination) to the last study visit (Visit 5 for Groups 1, 2, and 3 and Visit 6 for Group 4, occurring 30 days [+21 days] after the last vaccination), including occurrence, nature (MedDRA preferred term), time of onset, duration, intensity, action taken, relationship to the product administered, whether the event caused termination from the study, outcome, elapsed time from last administration (if less than 24 hours), relationship to study procedures, and seriousness criterion.

5.1.6 Complementary Output

5.1.6.1 Sensitivity Analysis due to COVID-19 Pandemic

The impact of COVID-19 pandemic situation on study conduct will be summarized through impact on visit procedures, study completion and major/critical protocol deviations due to COVID-19.

The subset of subjects who were impacted by COVID-19 is defined as the subjects with at least one major/critical protocol deviation due to COVID-19 or who did not complete the study due to COVID-19.

If more than 10% of subjects are impacted as per this definition, baseline and demographics characteristics, and the main immunogenicity and safety endpoints will also be summarized in the subsets of subjects impacted / non-impacted subjects to assess the potential impact of COVID-19 situation on study outcome. The outputs will be provided in Appendix 15 of the CSR.

The assessment of the impact COVID-19 pandemic will be based on but not limited to the following analysis:

- To summarize the impact of COVID-19 on the overall study conduct
 - Early termination due to COVID-19
 - Impact on visit conduct (visit not done, partially done, data collection method/procedure change)
 - Major and critical protocol deviations due to COVID-19

- To summarize disposition across study visits for subjects impacted/not impacted by COVID-19
- To summarize baseline demographics by randomized group for subjects impacted /not impacted by COVID-19
- To provide an individual listing of subjects impacted by COVID-19 and how they were impacted
- To provide a listing of visits impacted by COVID-19 and how they were impacted
- To assess the potential impact of COVID-19 on the main immunogenicity and safety endpoints in the subsets of impacted/non-impacted subjects

The main immunogenicity and safety endpoints that might be summarized are described as follows:

Immunogenicity analyses

The sensitivity analyses due to COVID-19 Pandemic in immunogenicity will be performed on PPAS and full analysis set (FAS).

- 1) The primary endpoint for immunogenicity will be assessed:
 - GMTs against meningococcal serogroups A, C, W, and Y measured by hSBA a 3-dose series vaccination at 12 to 18 months of age (Group 1 versus Group 2)
- 2) The secondary endpoint for immunogenicity will be assessed:
 - Antibody titers $\geq 1:8$ against meningococcal serogroups A, C, W, and Y measured by hSBA assessed after a 2-dose series at 5 months of age (Group 1 and Group 2)

Safety analyses

Safety overview after any vaccine injections – Overall Safety Analysis Set

Safety overview after vaccine injections at 2 months of age – Safety Analysis Set 1

Safety overview after vaccine injections at 4 months of age – Safety Analysis Set 2

Safety overview after vaccine injection at 6 months of age – Safety Analysis Set 3

Safety overview after vaccine injections at 12 through 18 months of age – Safety Analysis Set 4

5.1.6.2 Subgroup analysis

Additional subgroup analyses by gender, age group and pre-term/full term birth based on PPAS will be provided for primary and main secondary immunogenicity endpoints.

The gender subgroup analyses will have two categories (Female and Male). For the age group analysis, two categories will be used (≥ 42 to ≤ 59 days vs ≥ 60 to 89 days). Pre-term birth will be defined as birth with a gestational age < 37 weeks.

The following parameters will be assessed 30 days after the last vaccination in the second year and 30 days after the last vaccination in infant series:

- 1) The primary endpoint for immunogenicity will be assessed:
 - GMTs against meningococcal serogroups A, C, W, and Y measured by hSBA a 3-dose series vaccination at 12 to 18 months of age (Group 1 versus Group 2)
- 2) The secondary endpoint for immunogenicity will be assessed:
 - Antibody titers $\geq 1:8$ against meningococcal serogroups A, C, W, and Y measured by hSBA assessed after a 2-dose series at 5 months of age (Group 1 and Group 2)

The safety overview after any vaccine injections will be also described.

The subgroup analysis by pre-term/full term birth will be carried out only if there is minimum of 30 pre-term birth in the PPAS.

5.2 Analysis Sets

The study vaccines refer to MenACYW conjugate vaccine, Nimenrix® vaccine and concomitant routine vaccines in the pre-defined vaccination schedule from Visit 1 to Visit 4/Visit 5.

The investigational product only refers to MenACYW conjugate vaccine or Nimenrix® vaccine.

5.2.1 Full Analysis Set

There will be two Full analysis sets (FASs), one FAS for the primary series (FAS1) and one FAS for the booster vaccination (FAS2).

- FAS1 is defined as the subset of randomized subjects who received at least 1 dose of the study vaccine in the primary series and had a valid post-primary series vaccination blood sample result.
- FAS2 is defined as the subset of randomized subjects who received at least 1 dose of the study vaccine at booster vaccination and had a valid post-booster vaccination blood sample result.

5.2.2 Per-Protocol Analysis Set

The per-protocol analysis set (PPAS) is a subset of the FAS. There will be two PPAS: PPAS for the primary series (PPAS1) and PPAS for the booster series (PPAS2).

5.2.2.1 Per-Protocol Analysis Set for Primary Series (PPAS1)

The subjects presenting with at least one of the following relevant protocol deviations will be excluded from the PPAS1:

- Subject did not meet all protocol-specified inclusion criteria or met at least one of the protocol-specified exclusion criteria

- Subject did not complete the vaccination schedule
- Subject received a vaccine other than the one that he / she was randomized to receive
- Preparation and / or administration of vaccine was not done as per-protocol
- Subject did not receive vaccine in the proper time window
 - Visit 2: Visit 1 + 60 days (+14 days)
 - Visit 3 (Group 4 only): Visit 2 + 60 days (+14 days)
- Subject did not provide a post-dose serology sample in the proper time window or a post-dose serology sample was not drawn
 - Blood sampling 2 (BL0002):
 - Visit 3: Visit 2 + 30 days [+21 days] (Group 1, 2, 3)
 - Visit 4: Visit 3 + 30 days [+21 days] (Group 4)
- Subject received a protocol-prohibited therapy / medication / vaccine (identified among category 2 / category 3, not including the rotavirus vaccine administered at V1 and V2)
- Subject had other protocol violations that affected the subject's immune response, as determined by the clinical team before locking the database

In addition to the reasons listed above, subjects will also be excluded from the PPAS1 if their serology sample did not produce a valid test result (ie, results for all antigens are missing).

Vaccine correctness criteria apply to all the vaccines administered in the protocol (ie, MenACYW conjugate vaccine / Nimenrix® and the concomitants vaccines).

In the event of a local or national immunization program with a pandemic influenza or coronavirus vaccine or any other vaccine as needed, subjects who receive the one or more doses of a pandemic influenza or coronavirus vaccine at any time during the study will not be withdrawn from the study.

5.2.2.2 Per-Protocol Analysis Set for Booster Series (PPAS2)

The subjects presenting with at least one of the following relevant protocol deviations will be excluded from the PPAS2:

- Subject did not meet all protocol-specified inclusion criteria or met at least one of the protocol-specified exclusion criteria
- Subject did not complete the vaccination schedule
- Subject received a vaccine other than the one that he / she was randomized to receive
- Preparation and / or administration of vaccine was not done as per-protocol
- Subject did not receive vaccine in the proper time window for the booster dose at 12 to 18 months of age (all groups) and at least 180 days after Visit 2 (Group 1,2,3) or after Visit 3 (Group 4)

- Subject did not provide a post-dose serology sample in the proper time window or a post-dose serology sample was not drawn
 - Blood sampling 4 (BL0004):
 - Visit 5: Visit 4 + 30 days [+21 days] (Group 1, 2, 3)
 - Visit 6: Visit 5 + 30 days [+21 days] (Group 4)
- Subject received a protocol-prohibited therapy / medication / vaccine (identified among category 2 / category 3)
- Subject had other protocol violations that affected the subject's immune response, as determined by the clinical team before locking the database

In addition to the reasons listed above, subjects will also be excluded from the PPAS2 if their serology sample did not produce a valid test result (ie, results for all antigens are missing).

Vaccine correctness criteria apply to all the vaccines administered in the protocol, (ie, MenACYW conjugate vaccine / Nimenrix® and the concomitants vaccines). A licensed Measles, Mumps and Rubella vaccine must be received either during the study visit (Visit 4/Visit 5) or with a gap of at least 4 weeks before any study vaccines or after the end of the study. In the event of a local or national immunization program with a pandemic influenza or coronavirus vaccine or any other vaccine as needed, subjects who receive the 1 or more doses of a pandemic influenza or coronavirus vaccine at any time during the study will not be withdrawn from the study.

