6.7 Concomitant Medications and Other Therapies

At the time of enrollment, ongoing medications including but not limited to other therapies (eg, blood products), should be recorded in the source documents. All new medications prescribed for new medical conditions / AEs during study participation should also be recorded in the source documents.

Documentation in the CRB of concomitant medication(s) will be limited to specific categories of medications (Categories 1, 2, and 3 as detailed below). Those will include Category 1, 2, and 3 medications ongoing at the time of inclusion in the study, or started at any time during the subject's participation in the trial. For category 3 medication, the period of reporting in CRB will be restricted to only 3 days (72 hours) prior to each blood sampling time point.

Collection period in source documents

Reportable medications (Category 1, 2, and 3) will be collected in the source documents from the day of first vaccination to the end of the trial.^a

Categories of Reportable medications and reporting period

Reportable medications include medications that impact or may impact the consistency of the safety information collected after any vaccination and/or the immune response to vaccination.

- Category 1: medications with potential impact on the evaluation of the safety of the study vaccines. For example, antipyretics, analgesics, non-steroidal anti-inflammatory drugs (NSAIDs), systemic corticosteroids (therapy duration less than 2 weeks), and other immune modulators. Category 1 medications do not define the Per-Protocol Analysis Set (PPAS).

Note: Topical steroids (Inhaled, otic, ophthalmic, nasal etc.) should not be captured or reported.

Category 1 medications will be reported in the CRB from the day of first vaccination to the end of the solicited and unsolicited follow-up period after each vaccination. These medications will also be collected in the CRB for the 30- day period prior to the subsequent doses of the vaccine, wherever applicable (second, third, fourth, etc., in case of a multi-dose schedule with more than a 30-day interval between doses).

- Category 2: Reportable medications with potential impact on immune response of the study vaccines and used to define the Per-Protocol Analysis Set (PPAS). For example:
 - Flu vaccines administered within 14 days pre or post each study vaccine, including the day of the study vaccination visit

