 - Rotavirus vaccines administered within 14 days pre or post each study vaccination visit^b. Any vaccine other than study vaccines (vaccines non-described in the Protocol^c) within the 28 days (4 weeks) preceding or after the trial vaccination, including the day of the study vaccination visit
 - Immune globulins, blood or blood-derived products: used in the 3 months preceding the first blood draw and up to the last blood draw
 - Immunosuppressive therapy such as immune-suppressors, immune-modulators with immunosuppressive properties, long-term systemic corticosteroids therapy (prednisone or equivalent for more than 2 consecutive weeks) within past 3 months, anti-cancer chemotherapy, anti-proliferative drugs such as DNA synthesis inhibitors, or radiation therapy: used in the 6 months preceding the first trial vaccination, and up to the last blood draw.

^a Subject's parents will be required to document all medications received in the Diary Cards. The sites will focus on only recording the medications belonging to the 3 categories in the other source documents.

^b Subjects from Finland, Sweden and Poland can receive rotavirus vaccine concomitantly with study vaccinations at V1 and V2

^c if for any reason a study vaccine (PCV10, or PCV13 and/or Hexyon®/Hexacima®) is not administered concomitantly with investigation/control meningococcal vaccine, an interval of 4 weeks between this vaccination prior or following the investigational/control vaccine must be respected, otherwise, this vaccine administration out of the study will be considered as Category 2)

- Category 2 medications will be reported in the CRB during the study period up to the last blood draw.

In addition, the following vaccines should be recorded in the concomitant medication CRB as Category 2:

- Licensed Measles, Mumps and Rubella vaccines administered during the study participation (if MMR vaccination [including M-M-RVAXPRO®] occurred within the 28 days (4 weeks) preceding or after the trial vaccination visit, it will be used to define the PPAS definition)
- Licensed rotavirus vaccines received during the first year of life (if rotavirus vaccination occurred within the 14 days (2 weeks) preceding or after the trial vaccination visit, it will be used to define the PPAS definition)

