- Hepatitis B Vaccine received before the inclusion in the study (if Hepatitis B vaccination occurred within the 28 days (4 weeks) preceding or after the trial vaccination visit, it will be used to define the PPAS definition)
- Category 3: Systemic (Oral or injectable) antibiotics, as they may interfere with bioassays used for antibody testing when taken before a blood draw. Antibiotics that the subject received within 72 hours preceding each visit for blood draw related to IMP assessment (meningococcal vaccines) and used to define the PPAS. Category 3 medications will be reported in the CRB for the period of 3 days (72 hours) before each blood draw.

Note: Topical antibiotics (Inhaled, otic, ophthalmic, nasal, etc.) should not be captured or reported.

The information reported in the CRB for each reported medication will be limited to:

- Trade name
- Rationale for the origin of prescription: Whether it was a prophylactic^a medication? Prophylactic medications will be recorded in the Action Taken section of the AE collection tables.
- Medication category (1, 2, or 3)
- Start and stop dates

Dosage and administration route, homeopathic medication, will not be recorded.

If the subject has received medications other than those listed in Categories 1, 2, and 3, the detailed information will be collected in the source documents only.

Medications given to treat an AE will be captured in the “Action Taken” section of the AE CRB only. No details will be recorded in the concomitant medication CRB unless the medication(s) received belongs to one of the prelisted categories.

^a Medication(s) prescribed for preventing AE occurrence (e.g. paracetamol to reduce the risk of fever)

7 Management of Samples

Blood samples for the assessment of antibody responses will be collected and subjects in Groups 1, 2, and 3 will provide blood samples for immunogenicity assessment as follows:

- at baseline (pre-primary vaccination 1, Day 0)
- 30 days (+21 days) after the 2nd dose of MenACYW conjugate vaccine / Nimenrix®
- prior to the 3rd dose (toddler dose) of MenACYW conjugate vaccine / Nimenrix®
- 30 days (+21 days) after the 3rd dose (toddler dose) of MenACYW conjugate vaccine / Nimenrix®

Subjects in Group 4 will provide blood samples for immunogenicity assessment as follows:

- at baseline (pre-primary vaccination 1, Day 0)
- 30 days (+21 days) after the 3rd dose of MenACYW conjugate vaccine
- prior to the 4th dose (toddler dose) of MenACYW conjugate vaccine

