5.7 Changes in the Conduct of the Trial or Planned Analyses

The protocol stipulated that "The main immunogenicity analysis will be performed on the PPAS analysis set including PPAS2 for the primary objective and PPAS1 for secondary objective 1 and will be confirmed on the FAS2 and FAS1". However, due to an internal change of analysis process, the main immunogenicity analysis will be confirmed on the FAS2 and FAS1 only if the difference between PPAS1 and FAS1 (or PPAS2 and FAS2) is greater than 10%, as described in [section 5.2.5](#).

Concomitant medications category fields were inactivated, and concomitant medications were coded with WHODrug dictionary by the coding specialists.

Also, as participants in Group 3 and 4 have the same vaccines administered at 2, 4 and at 12 to 18 months of age, actual treatment group derivation for the Safety analysis sets for those groups had been specified in [section 5.2.3](#).

Finally, several analysis cut-offs for some concentrations have been considered in addition to the one already defined in the protocol:

- For anti-diphtheria antibody concentrations, the cut-off ≥ 1.0 IU/mL has been added for secondary objective 3 (30 days after Dose 2) and the cut-off ≥ 0.01 IU/mL has been added for secondary objective 3 (Before and 30 days after the booster dose) and secondary objective 6
- For anti-polyribosyl-ribitol phosphate (PRP) antibody concentrations, the cut-off ≥ 1.0 μ g/mL has been added for secondary objective 3 (30 days after Dose 2)

- For anti-tetanus antibody concentrations, the cut-off ≥ 1.0 IU/mL has been added for secondary objective 3 (30 days after Dose 2) and the cut-off ≥ 0.01 IU/mL has been added for secondary objective 3 (Before and 30 days after the booster dose) and secondary objective 6
- For anti-pneumococcal antibody concentrations for serotypes 1, 4, 5, 6B, 7F, 9V, 14, 18C, 19F, and 23F, the cut-off ≥ 1.0 μ g/mL has been added for secondary objective 3 and secondary objective 6

6 References List

- 1 Newcombe R.G., Two-sided confidence intervals for the single proportion: comparison of seven methods, *Statistics in Medicine*, (1998) 17, 857-872.

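### Do the per-protocol sets lose a usable exclusion rule because the medication category fields were switched off?

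*SAP*

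**What the plan says.** SAP 5.2.2.1 (PPAS1) and 5.2.2.2 (PPAS2) list the deviations that remove a child from each set. In PPAS2 one of them reads "Subject received a protocol-prohibited therapy / medication / vaccine (identified among category 2 / category 3". PPAS1 has the same criterion but adds an exemption for rotavirus vaccine given at Visits 1 and 2. Protocol 12.2.8.1 and 12.2.8.2 differ in the same way.

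Protocol 6.7 defines the categories. For each medication reported in the case report book it lists the items recorded, among them the trade name, the start and stop dates, and "Medication category (1, 2, or 3". SAP 5.7 reports a later change: "Concomitant medications category fields were inactivated, and concomitant medications were coded with WHODrug dictionary by the coding specialists".

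Under Protocol 12.2.9, PPAS2 is the main set for the primary objective and PPAS1 for secondary objective 1. SAP 5.7 also makes the confirmatory analysis on the full analysis set conditional: it is done "only if the difference between PPAS1 and FAS1 (or PPAS2 and FAS2) is greater than 10" percent.

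**The concern.** On a first reading the exclusion criterion appears to rest on a data item that is no longer collected. WHODrug coding says what a product is. It does not say which protocol category the product falls in, and the categories also depend on timing: 14 days, 28 days, 3 months and 6 months for Category 2, and 72 hours for Category 3. The SAP supplies no code list, window algorithm or named reviewer.

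Three details add to the worry:

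- Immune modulators appear under two categories. One affects per-protocol membership and the other does not ("Category 1 medications do not define the Per-Protocol Analysis Set (PPAS").
- "Licensed rotavirus vaccines received during the first year of life" are all recorded as Category 2, although only some of them count for the per-protocol set.
- The rotavirus exemption is written into PPAS1 and not into PPAS2.

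If two programmers could build different versions of PPAS2, the primary analysis set would not be fully specified. Membership also feeds the 10% rule that decides whether a full-analysis-set check is run.

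**Working it through.** **1. What the criterion depends on.** The bullets in SAP 5.2.2.1 and 5.2.2.2 name categories; they do not name a form field. Protocol 6.7 defines those categories, and switching off the field leaves that definition in place.

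**2. Whether the categories can be rebuilt.**

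- Influenza, rotavirus and other vaccines (Category 2): the coded product, its date and the study visit dates give the 14-day and 28-day windows.
- Blood products and immunosuppressive therapy (Category 2): the product and start and stop dates give the 3-month and 6-month windows. The same dates separate steroid courses longer than 2 weeks (Category 2) from shorter ones (Category 1).
- Systemic antibiotics (Category 3): the product, its dates and the blood-draw date give the 72-hour window. Route is not recorded, but Protocol 6.7 tells sites not to report topical antibiotics, so route is not needed.

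**3. The apparent overlap.** Category 1 covers "systemic corticosteroids (therapy duration less than 2 weeks), and other immune modulators". Category 2 covers "immune-modulators with immunosuppressive properties". The qualifier about immunosuppressive properties separates them. Applying it takes a medical judgement on the product.

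**4. Rotavirus recorded versus rotavirus counted.** Protocol 6.7 gives the rule directly: every first-year dose is recorded, and a dose bears on the per-protocol set if it falls within 14 days of a study vaccination visit.

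**5. The different exemption.**

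- Finland, Sweden and Poland: Protocol 5.2.5 (exclusion criterion 2), 5.2.7.1 and the footnote in 6.7 permit rotavirus vaccine at Visits 1 and 2. The PPAS2 criterion applies to prohibited products, so these children stay in PPAS2 without an explicit exemption.
- Czech Republic and Romania, which also supply Groups 1 and 2: a 2-week gap is required. If a same-day dose was planned at enrolment, the child met exclusion criterion 2 and leaves both sets under the eligibility bullet.
- What remains is an unplanned, off-protocol dose in those two countries, which read literally would stay in PPAS1 and leave PPAS2. Protocol 6.3.1 has sites source rotavirus vaccine only in Finland, Sweden and Poland, so few such doses are expected.

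**6. Scale.** Inputs from SAP 5.5: 528 evaluable per arm, margin 1.5 (log10 = 0.1761), log10 SDs of 0.7, 0.7, 0.5 and 0.6 for A, C, Y and W, one-sided alpha 2.5%, true ratio 1.

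Power per serogroup = Φ(0.1761 / (SD × √(2/n)) − 1.96)

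- n = 528: A 0.9833, C 0.9833, Y 0.9999, W 0.9975. The product is 0.9644. The plan states 96.2%, which is what its rounded table entries give: 0.983 × 0.983 × 0.999 × 0.997 = 0.962.
- n = 421: product 0.9005. n = 420: 0.8995. So 528 − 421 = 107 children per arm can be lost before joint power falls below 90%.

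The 10% rule is (FAS2 − PPAS2) / FAS2 > 0.10. With 2 × 528 = 1,056 children from Groups 1 and 2 in PPAS2, 117/1,173 = 9.97% does not trigger it and 118/1,174 = 10.05% does. Those 118 are exclusions for any reason, so the figure describes the rule and does not measure the effect of category assignment. The documents give no count of Category 2 or 3 exclusions.

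**The case for a change.** The strongest reply is that the other changes in SAP 5.7 come with their replacement: the full-analysis-set condition points to 5.2.5, the Group 3/4 derivation to 5.2.3, and the added cut-offs are listed. This one does not. The SAP also revised the PPAS2 list elsewhere, adding the 180-day interval after Visit 2 for Groups 1 to 3, yet left this bullet alone.

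Some discretion also remains. The Category 2 list in Protocol 6.7 is illustrative. The PPAS2 bullet does not say whether antibiotics before an earlier blood draw exclude a child whose primary sample is BL0004. Blind review is a process, and the SAP does not say that it assigns the categories.

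The observation about the missing sentence stands. The discretion, however, was not created by switching off the field. An open Category 2 list and the question of which blood draws count would have been there with a site-entered category too, and that entry would have been made separately at about 50 sites. Protocol 11.3 and SAP 5.6 provide for a blind data review before lock, with statistical input. Both per-protocol definitions already leave other violations affecting immune response to the clinical team before lock. Differential handling of the two arms is therefore unlikely.

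The argument about the 10% rule needs the trial to sit close to the threshold. Nothing in the documents shows that it does.

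**Conclusion.** No change follows. The SAP omits a sentence saying how categories 2 and 3 are assigned once the field is gone, and analysts can fill that gap sensibly from Protocol 6.7, the coded product and the recorded dates. The immune-modulator wording distinguishes its two categories, the rotavirus counting rule is written down, and the different exemption matters only for an unplanned, off-protocol dose in two countries.

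The size of the effect cannot be computed, because no count of such exclusions is given; it is probably small. No result or conclusion is shown to be wrong if the plan is followed as it stands. This rests on three assumptions: trade names and dates continued to be collected as Protocol 6.7 specifies, the assignments are made blind before database lock, and the criterion is read as applying to prohibited products, as its wording says.

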12.2.9 Populations Used in Analyses

The main immunogenicity analyses will be performed on the PPAS analysis set including PPAS2 for the primary objective and PPAS1 for secondary objective 1, and will be confirmed on the FAS2 and FAS1. In the FAS1 and FAS2, subjects will be analyzed by the vaccine group to which they were randomized.

The safety analysis will be performed on the SafAS, SafAS1 to SafAS 4. Subjects will be analyzed according to the vaccine they actually received.

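### Does the rotavirus exemption missing from the PPAS2 definition remove permitted recipients from the primary analysis?

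*SAP*

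**What the plan says.** SAP 5.2.2.2 and Protocol 12.2.8.2 list the deviations that remove a subject from PPAS2. One of them is "Subject received a protocol-prohibited therapy / medication / vaccine (identified among category 2 / category 3"), and the bullet ends there. The corresponding PPAS1 bullet (SAP 5.2.2.1, Protocol 12.2.8.1) has the same opening but qualifies the parenthesis: "identified among category 2 / category 3, not including the rotavirus vaccine administered at V1 and V2". Protocol 12.2.9 assigns "PPAS2 for the primary objective and PPAS1 for secondary objective 1".

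The categories are defined in Protocol 6.7, where rotavirus vaccine appears twice under Category 2:

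- The first item is "Rotavirus vaccines administered within 14 days pre or post each study vaccination visit". Its footnote adds: "Subjects from Finland, Sweden and Poland can receive rotavirus vaccine concomitantly with study vaccinations at V1 and V2".
- The second, among the vaccines to be recorded, says "if rotavirus vaccination occurred within the 14 days (2 weeks) preceding or after the trial vaccination visit, it will be used" to define the per-protocol set. It has no footnote and does not say which of the two sets it means.

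The permission for same-visit rotavirus vaccine in those three countries also appears in Protocol 5.1.1, 5.1.3, 5.2.5 (criterion 2) and 5.2.7.1, and in SAP 3.1.

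**The concern.** Two nearly identical rules differ by one clause, and the clause is missing from the set that carries the primary objective. A programmer working from the two bullets might infer that the difference is deliberate: if calling a vaccine prohibited were enough to spare permitted recipients, PPAS1 would not need an exemption. The unfootnoted second rotavirus entry in Protocol 6.7 could support that inference.

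At stake would be infants who followed an allowed schedule. Finland, Sweden and Poland are three of the five countries that supply Groups 1 and 2. Protocol 5.1.2 singles out Finland as the one primary-objective country with a widely implemented, publicly funded rotavirus programme, with coverage above 90%. Dropping recipients would cost precision and thin out those countries in the primary analysis. It should not bias the comparison, because randomization is 1:1 within center (Protocol 6.5) and Groups 1 and 2 are blinded (Protocol 6.4).

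**Working it through.** **Does the text exclude permitted recipients?**

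1. *Scope of the rule.* The PPAS2 list is introduced as a list of relevant protocol deviations, and this bullet is confined to what the protocol prohibits. A rotavirus dose at Visit 1 or 2 in Finland, Sweden or Poland is neither a deviation nor prohibited.
2. *First Category 2 entry.* The footnote granting the permission is attached to the rotavirus item itself, so the category definition carries it into any set that uses the category.
3. *Visit day.* The influenza item reads "Flu vaccines administered within 14 days pre or post each study vaccine, including the day of the study vaccination visit", and the item for any other vaccine reads "within the 28 days (4 weeks) preceding or after the trial vaccination, including the day of the study vaccination visit". Neither rotavirus entry names the visit day. The any-other-vaccine item does not catch rotavirus either, since it is limited to vaccines not described in the protocol.
4. *Second Category 2 entry.* It speaks of the per-protocol set in general. In PPAS1 that general rule plainly gives way to the Visit 1 and 2 permission, and nothing in the entry treats PPAS2 differently.
5. *Placement.* PPAS1 checks the infant vaccination windows and the post-infant sample (BL0002). PPAS2 checks the booster window and the post-booster sample (BL0004). Visits 1 and 2 belong to the infant series, so PPAS1 is the natural place for the clause. This is supportive only, because some PPAS2 criteria, such as eligibility and schedule completion, cover the whole study.

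**What if the infants were dropped anyway?**

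Inputs (Protocol 12.5, SAP 5.5): 716 enrolled per arm, 26.2% lost from the per-protocol set, 1-sided alpha 2.5%, margin 1.5, SD of log10 titer 0.7 (A), 0.7 (C), 0.5 (Y) and 0.6 (W). As in the plan's calculation, the true GMT ratio is taken as 1.

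Evaluable per arm: 716 × (1 − 0.262) = 528.4, so 528.

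Power per serogroup = Φ( log10(1.5) / (SD × √(2/n)) − 1.96 ), with log10(1.5) = 0.1761. Overall power is the product over the four serogroups.

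At n = 528, serogroup A: 0.1761 / (0.7 × √(2/528)) − 1.96 = 4.09 − 1.96 = 2.13, giving 98.33%. C is the same, Y is 99.99% and W is 99.75%. The product is 96.4%. The stated 96.2% is the product of the rounded table entries: 0.983 × 0.983 × 0.999 × 0.997 = 0.962. The plan's figure is reproduced.

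Assumed further loss from the 528:

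| Loss | n per arm | Overall power |
|---|---|---|
| 0% | 528 | 96.4% |
| 5% | 502 | 95.4% |
| 10% | 475 | 94.0% |
| 20% | 422 | 90.1% |
| 30% | 370 | 84.1% |

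Power first falls below 90% at n = 420, a loss of 1 − 420/528 = 20.5%. If only Finland contributed, with 90% of its infants vaccinated and all of them at the study visits, the Finnish share of Groups 1 and 2 would have to be about 20.5/90 = 22.7%. For comparison, an equal split over five countries is 20%, which gives a loss of 0.20 × 0.90 = 18%, n = 433 and power of 91.1%. These shares are assumptions. Doses given at the allowed two-week gap would reduce the loss; same-visit use in Sweden or Poland would increase it.

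**The case for a change.** The best argument for a change is that the wording matters more than usual here. PPAS1 contains the same reference to prohibition and still states the exemption, so its absence from PPAS2 invites a contrast. The PPAS2 bullet has no time limit. SAP 5.7 records that the medication category fields were inactivated, so Category 2 status has to be worked out from the written rule and coded products. The SAP also repaired another PPAS2 bullet, adding the 180-day interval for Groups 1 to 3 that Protocol 12.2.8.2 gave only for Group 4. Adding one more clause would cost almost nothing, and the FAS2 analysis is only supplemental and runs only if PPAS2 and FAS2 differ by more than 10%.

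The asymmetry is real, and so is the point about deriving the category. The rest carries less weight. The PPAS1 bullet has no time limit either; both sets take their limits from Protocol 6.7. Silence in SAP 5.7 shows nothing, because the SAP bullet repeats the protocol and there was no change to record. Read in full, Protocol 6.7 leads an analyst to keep these infants. A wholesale loss of one country's infants would be hard to miss in the data review before database lock, which includes a statistical review (SAP 5.6). Nor is copying the PPAS1 clause wholly neutral: it names no country, so it would also spare same-visit doses in the Czech Republic and Romania, which the permission does not cover.

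**Conclusion.** No change to the plan follows. PPAS1 states an exemption that PPAS2 leaves unsaid, but PPAS2 removes only subjects with prohibited vaccines, and permitted rotavirus vaccine at Visits 1 and 2 is not one of those. Under that reading the primary analysis set is unaffected.

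The conclusion rests on analysts applying the category definition in Protocol 6.7 together with its footnote, which is what a careful reading requires. If they did not, the effect would be lost precision and country representation, with no differential bias expected. Power would stay at or above 90% up to a loss of about 20% per arm. Whether a loss of that size could occur cannot be judged from the documents, since enrolment by country and same-visit uptake are not given. Repeating the permission in the PPAS2 bullet would be harmless tidying if limited to the three countries, but the analysis does not depend on it.
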